8.2.2. Analysis of Secondary Endpoints

A secondary efficacy parameter is Responder Rate, defined as subjects who have a $\geq 50\%$ reduction from baseline in partial seizure rate during the double-blind 48 hour Video-EEG period. Subjects meeting this criterion will be considered responders.

Subjects who do not meet the favorable responder definition will be considered non-responders. The dichotomized Responder variable will be analyzed using a logistic regression model via maximum likelihood estimation with the following covariates:

- *treatment group, as a fixed effect;*
- *age stratum, as a fixed effect;*
- *geographical region (as defined in Table 2 above) by pooling of investigator centers, as a fixed effect. If any non-treatment factor causes non-convergence of the model, that factor will be dropped from the model.*

Comparisons will be performed for each pregabalin dose relative to placebo using a maximum likelihood tests and confidence intervals. The definitive statistical summary for treatment group comparisons will be the odds ratios.

The responder outcomes will be summarized descriptively by treatment group using counts and percentages.

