The blinded sample size re-estimation procedure for this study originally did not allow for a reduction in the planned sample size of 123 subjects, nor did it pre-specify any cap to the suggested increase in sample. The procedure was conducted by a statistician not associated with the study during its conduct or during the final analysis. There was no penalty applied to the final analysis p-values or confidence intervals for assessing treatment difference from placebo due to this blinded sample size re-estimation procedure. Details of the sample size re-estimation procedure are included in the Statistical Analysis Plan.

The blinded sample size re-estimation procedure utilized for this study was revised per Statistical Analysis Plan and did not allow for a reduction in the planned sample size of 123 subjects total or require an increase in sample size greater than 150 subjects. The following decision rules were utilized for the blinded sample size re-estimation:

- a. If the recalculated sample size is less than or equal to the original sample size of 123 subjects total, then the sample size will not be adjusted.
- b. If the recalculated sample size is greater than the original sample size (123 subjects total) then the following information will be considered:
 - If the re-estimated sample size is between 123 and 150, then the sample size will be adjusted to the re-estimated sample size.
 - If the re-estimated sample size exceeds 150 then the sample size will be increased to 150.

The blinded sample size re-estimation was conducted, and the sample size will be increased to approximately 150 subjects.

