2.1. Study Design

[figure not shown]
Study A0081042 is a double-blind, placebo-controlled, randomized, parallel group, multicenter study to evaluate efficacy and safety of two dose levels of pregabalin compared to placebo administered TID as adjunctive therapy in pediatric subjects 1 month (44 weeks gestational age) through <4 years of age with partial onset seizures with or without secondary generalization.

The study is composed of 4 phases:

- Video-Electroencephalographic (EEG) baseline phase with a target minimum of 48 hours. To ensure that the target minimum of 48 hours of Video-EEG is obtained, the total duration of the Video-EEG baseline phase will be up to 72 hours.
- 5 day double-blind dose escalation phase.
- 9 day double-blind fixed dose treatment phase, which includes a Video-EEG evaluation over the final 3 days at the end of this 9-day phase with a target minimum of 48 hours and a total recording duration of up to 72 hours. For subjects who successfully complete the target 48 hour Video-EEG or must terminate the Video-EEG recording before the end of this 9-day phase, fixed dosing will continue until beginning the taper phase.
- 7 day double-blind taper phase.

The total double-blind treatment phase is 21 days.

Study Design Diagram:

* Eligible subjects may be assessed for screening into study A0081106 and complete end of study activities for A0081042 at Visit 7 (V7)

^a [3 mg/kg/day for subjects 1 to 3 months of age];

^b [6 mg/kg/day for subjects 1 to 3 months of age];

^c [12 mg/kg/day for subjects 1 to 3 months of age]

Statistical Power and Sample Size

NOTE: Because the following sample size work occurred prior to study conduct and prior to review of blinded data, this section remains unchanged with respect to the constant 1/28 in the log transformation of the 24-hour seizure rate data and the differences between pregabalin and placebo.

A total of approximately 123 subjects will be randomized in this study in a 2:2:1 ratio of placebo, Level 1 and Level 2. This randomization scheme will allow a sufficient number of patients to be studied at each dose level for safety, while providing adequate power of the study to detect a significant effect for dose Levels 1 and 2. Randomization of 123 subjects accounts for a 10% discontinuation rate, with a resulting sample size of the necessary 110 subjects (44 placebo, 44 Level 1, and 22 Level 2).

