The sample size rationale is based on the observed difference in \log_e (double-blind 24-hour seizure rate $+\frac{1}{28}$) between pregabalin and placebo. A difference in the least squares means between pregabalin and placebo was estimated to be -0.668 and -0.448 for 600- and 300 mg doses respectively, with a pooled standard deviation (SD) of 0.73. This difference and pooled SD was obtained from a meta analysis of the -34, -11, -09 study data in adult subjects with partial onset seizures.

For the purposes of this study, the same SD is also used to assess the power and sample size requirements for comparing each pregabalin group to placebo. While every effort will be put forth to minimize the variability in conducting this study, a larger than anticipated SD may actually be observed. To address this potential concern, a blinded sample size re-estimation procedure will be applied when approximately two thirds of the subjects that make up initial sample size have the opportunity to complete the study. Details of the sample size re-estimation procedure will be included in [Appendix 2.1.1](#).

Table 1. Power Calculations and Sample Size Assumptions for the Primary Endpoint

$$(\log_e (24\text{-hour seizure rate} + \frac{1}{28}))$$

Comparison	Log Transformed Difference from Placebo	Percent Difference from Placebo	Number of Pregabalin Subjects	Number of Placebo Subjects	SD (log transformed 24-hour seizure rate)	Power
Expected difference ¹ between Level 2	-0.668	-48.7%	22	44	0.73	0.932
Expected difference ¹ between Level 1	-0.448	-36.1%	44	44	0.73	0.812

¹ Expected difference is the observed difference between the specified pregabalin dose minus placebo based on a meta analysis of studies -009, -011, and -034 based on the log transformed 24-hour seizure rate.

Level 1 and Level 2 doses are anticipated to result in exposure that approximates 300 mg/day and 600 mg/day, respectively, achieved in adults.

In order to address the primary analysis comparison between placebo and the Level 2 dose group, a sample size of 44 subjects in the placebo group and 22 subjects in the Level 2 dose group will provide at least 90% power to detect a true difference of -0.668 using a two-sided test at the 0.05 level of significance with a standard deviation of 0.73.

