8.2. Statistical Analyses

8.2.1. Analysis of Primary Endpoints

The primary analysis will be performed on the primary endpoint, \log_e (double blind 24-hour EEG seizure rate +1), using a linear model with treatment, age stratum, and geographical region (as defined in Table 2 above) as fixed factor effects, and \log_e (baseline 24-hour EEG seizure rate +1) as a continuous covariate. This linear model will include both dose groups of pregabalin. This analysis will be applied for all subjects who satisfy mITT criteria and for data of observed case.

Each dose of pregabalin and placebo will be compared using a sequential step-wise testing procedure. For this analysis, the following steps will be applied:

- *Step 1: Test the difference between the Level 2 group and placebo.*
 - $H_{01}: \mu_{\text{Level 2}} - \mu_{\text{Placebo}} = 0$
 - $H_{a1}: \mu_{\text{Level 2}} - \mu_{\text{Placebo}} \neq 0$
- *Step 2: Test the difference between the Level 1 group and placebo.*
 - $H_{02}: \mu_{\text{Level 1}} - \mu_{\text{Placebo}} = 0$
 - $H_{a2}: \mu_{\text{Level 1}} - \mu_{\text{Placebo}} \neq 0$

If H_{01} is rejected ($p \leq 0.05$) then move to step 2, otherwise claim no difference and stop. If H_{02} is rejected ($p \leq 0.05$) then claim a difference for all the comparisons, otherwise claim differences between 14 mg/kg/day and placebo only.

Least square means will be calculated using the observed marginal distribution. Two-sided 95% confidence intervals of the difference between the least square means will be calculated by using the appropriate least square means and their standard errors. Results will be reported as “percent reduction in seizures” relative to placebo. For example, a difference between one of the pregabalin doses and placebo of -0.400 on the log transformed scale for the 24-hour seizure rate, translates into a 33% reduction in the 24-hour seizure rate of the pregabalin group from the placebo group (ie, $100\% \times [\exp^{-0.400} - 1] = -33\%$).

An additional back transformation will be calculated for percent reduction in seizures for each pregabalin treatment group relative to placebo for presentation in the CSR as

$$\text{follows: } 100\% \times \frac{[\exp(\text{LSMean(pregabalin)}) - 1] - [\exp(\text{LSMean(placebo)}) - 1]}{\exp(\text{LSMean(placebo)}) - 1}$$

Sensitivity Analysis

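### The responder model omits the log baseline seizure rate used in the primary model, so a chance baseline difference in the small Level 2 arm goes unadjusted in the odds ratio (minor)

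*SAP*

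**What the plan says.** For the responder endpoint, SAP 8.2.2 says: "The dichotomized Responder variable will be analyzed using a logistic regression model via maximum likelihood estimation with the following covariates". The list is treatment group, age stratum and region. SAP 6.4, 8.1.3 and 8.2.4 and Protocol 9.2.2 give the same set. The odds ratio is the main reported comparison. SAP 8.1.3 and 8.2.2 allow a non-treatment factor to be dropped if it stops the model converging.

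The primary model in SAP 8.2.1 has the same factors and adds, on the log scale, the "baseline 24-hour EEG seizure rate +1) as a continuous covariate". SAP Appendix 2.1.1 groups baseline rate, age strata and region together as terms that explain variability in the seizure data.

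A responder is a child whose 24-hour rate falls by at least half from his or her own baseline (SAP Appendix 1). Membership of the mITT set requires a baseline recording with at least one partial seizure and at least 24 evaluable hours (SAP 5.1), so the covariate is never missing there. Tests outside the primary step-wise procedure are at the nominal level (SAP 4.2).

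Allocation is "in a 2:2:1 ratio of placebo, Level 1 and Level 2" (SAP 2.1). After the blinded re-estimation, "the sample size will be increased to approximately 150 subjects" (Protocol 9.1).

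**The concern.** Two of the three terms named in Appendix 2.1.1 enter the responder model. The third is left out with no reason given, and no sensitivity analysis of the responder endpoint adjusts for it.

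Dividing by baseline does not make response independent of baseline. Children are selected on a minimum count over about 48 hours, so the counts can be small and subject to regression to the mean. The chance of a 50% fall can then depend on the baseline level in every arm. If it does, and Level 2 happens to start higher or lower than placebo, part of the responder odds ratio reflects that accident. The primary comparison is adjusted for such a difference, so the two efficacy results could diverge for a reason unrelated to treatment.

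**Working it through.** **1. The plan's own power figures.** SAP 2.1 gives differences "estimated to be -0.668 and -0.448 for 600- and 300 mg doses respectively, with a pooled standard deviation (SD) of 0.73", "using a two-sided test at the 0.05 level of significance with a standard deviation of 0.73". With noncentrality = |difference| / (SD × √(1/n₁ + 1/n₂)):
- Level 2, 22 vs 44: 0.668 / (0.73 × 0.261) = 3.50 on 64 df, power 0.932.
- Level 1, 44 vs 44: 0.448 / (0.73 × 0.213) = 2.88 on 86 df, power 0.812.

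Both match SAP Table 1. They concern the primary endpoint. The documents state no responder rate, odds ratio or responder power, so every responder input below is an assumption.

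**2. Arm sizes.** "Randomization of 123 subjects accounts for a 10% discontinuation rate": 110 / 0.9 = 122.2, rounded up to 123. At 150 randomised, Level 2 has 150 × 1/5 = 30, and 30 × 0.9 = 27 analysable. Placebo has 150 × 2/5 = 60, and 60 × 0.9 = 54.

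**3. Chance imbalance, in SD units of log baseline.** SE = √(1/27 + 1/54) = 0.236. P(|difference| > 0.3) = 2 × [1 − Φ(0.3/0.236)] = 20%, and P(|difference| > 0.5) = 3%. At 22 vs 44 these are 25% and 6%.

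**4. Effect on the odds ratio.** The unadjusted log odds ratio shifts by about (baseline coefficient per SD) × (imbalance in SD). At an imbalance of 0.3 SD:

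| Assumed coefficient per SD | Shift in log OR | OR multiplied by |
|---|---|---|
| −0.74 | −0.222 | 0.80 |
| −0.38 | −0.114 | 0.89 |
| 0 | 0 | 1.00 |
| +0.39 | +0.117 | 1.12 |
| +0.50 | +0.150 | 1.16 |

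The SE of the Level 2 log odds ratio is about 0.50 (step 5), so a shift of 0.15 is about 0.3 of one SE.

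**5. Simulation with the link assumed directly.** 54/54/27 children, placebo response 30% at mean baseline, Level 2 log OR 1.1, 4,000 trials per setting, age and region terms left out. Each cell shows the model without / with baseline:

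| Coefficient per SD | Mean log OR | Mean SE | Power | Type I error (true log OR 0) |
|---|---|---|---|---|
| 0 | 1.12 / 1.13 | 0.498 / 0.502 | 0.626 / 0.628 | 0.047 / 0.047 |
| 0.25 | 1.11 / 1.13 | 0.498 / 0.507 | 0.608 / 0.616 | 0.043 / 0.045 |
| 0.5 | 1.08 / 1.15 | 0.497 / 0.517 | 0.590 / 0.609 | 0.039 / 0.045 |
| 1.0 | 0.94 / 1.15 | 0.492 / 0.553 | 0.474 / 0.546 | 0.046 / 0.047 |

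Adjustment raises the SE and also moves the log odds ratio away from zero. Power rises by about 1 to 2 points for a weak to moderate link and about 7 for a strong one.

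**6. Simulation from counts.** Here 48-hour counts with at least 2 baseline seizures were generated and response derived as a fall of at least 50% (1,500 trials per setting). The fitted baseline coefficient ran from −0.38 to +0.39 per SD. Power changed by −1.0 point (0.921 to 0.911) to +1.2 points (0.651 to 0.663). A placebo-only set with wider assumptions gave coefficients from about −0.74 to +0.41 per SD. Further count simulations put the power change at about −0.3 to +3 points. Gains of up to 4.6 points appeared only when an SD of 1.0 replaced the planned 0.73. Differences of a point or less are close to simulation error.

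**The case against.** The omission is deliberate in form: SAP 6.4 assigns the log baseline rate to the primary and similar parametric models, and age and region to the responder model. The outcome is already relative to each child's baseline, so the remaining link may be weak. The test is nominal and secondary, and a baseline-adjusted primary analysis sits beside it. Consistency is not a reason for the choice, however, and step 6 shows that the remaining link need not be zero. The argument limits the size of the point but does not remove it.

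Readers might infer three stronger claims, none of which the documents support:
- **That omission costs precision, as in a linear model.** In logistic regression the SE of the treatment log odds ratio rises when a prognostic covariate is added (0.497 to 0.517 at 0.5 per SD). What omission can cost is power, usually little.
- **That the unadjusted analysis is biased or anti-conservative.** Imbalance is random. Type I error without baseline was 0.039 to 0.047 in step 5.
- **That adding the term leaves the reported quantity untouched.** The odds ratio is already conditional on age and region. Conditioning on baseline as well can change its value even under perfect balance (1.08 to 1.15 on the log scale at 0.5 per SD).

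It also stands that the model already has six non-intercept parameters (two each for treatment, age and region) and a drop rule, so a seventh term needs a stated place in that rule.

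**Conclusion.** The point holds as a minor one. The responder model leaves unadjusted a chance baseline difference that the primary model handles, in a comparison of about 27 with 54 children. The 16% illustration rests on an assumed coefficient of 0.5 per SD, somewhat above the positive values in step 6. With coefficients from −0.38 to +0.39, the same 0.3 SD imbalance multiplies the odds ratio by 0.89 to 1.12, and at zero there is no shift. The power change is about −1 to +3 points under the count-based assumptions at the planned variability. The benefit is protection against chance imbalance and perhaps slightly more power. It is not a smaller SE or better type I error control, and no confirmatory claim depends on it.

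The arm sizes assume that 10% loss covers every reason for leaving the mITT set.

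**What to change.** Before unblinding:
- Add log_e(baseline 24-hour EEG seizure rate + 1) as a pre-specified continuous covariate to the responder model in SAP 6.4, 8.1.3, 8.2.2 and 8.2.4, and align Protocol 9.2.2. Changing only the Section 8 entries would leave SAP 6.4 contradicting them.
- State that the odds ratio is conditional on age stratum, region and baseline rate.
- State how the baseline term is treated under the non-convergence rule, including the order in which terms may be dropped.

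If the sponsor prefers to keep the present model as the main responder analysis, a pre-specified baseline-adjusted sensitivity analysis would meet most of the point.

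The cost is one model term and an odds ratio with a slightly different conditional meaning. No new data are needed.

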8.2.3. Analysis of Safety Data

All subjects with at least 1 dose of study medication will be included in the safety analyses. Baseline assessments are done at Day 1 (Visit 3). If Visit 3 data is missing the last available observation prior to start of study treatment is considered as baseline.

No inferential safety analyses are planned. Pfizer safety reporting standards will be utilized for all safety endpoints.

In addition, a summary of the number of days in the study will be presented for each treatment group.

8.2.3.1. Adverse Events

All AEs occurring during the course of the study will be coded using MedDRA coding dictionary.

All AEs (serious and non-serious) reported during the course of this study from the first day of study treatment through and including 999 calendar days after the last administration of the study drug will be considered treatment emergent AEs (TEAEs). Only AEs captured in this study will be included, and not AEs captured in the 1-year open label safety study.

An overall summary of treatment-emergent AEs will be provided. Treatment-emergent AEs will also be summarized by system organ class, preferred term, severity, and relationship to study drug. Summaries and listings of all AEs, SAEs and treatment-related AEs will be

presented in accordance with the current Pfizer Standard Operating Procedures (SOPs) and Best Practices.

The 3-tier Approach for summarizing AEs will be implemented, and events (MedDRA PTs) will be classified into the following tier definitions:

Tier 1: None

Tier 2: Targeted Medical Events (TMEs) identified in the Lyrica Safety Review Plan

- Point estimates and confidence intervals for the risk difference. Risk Difference is computed as Level 1 versus Placebo and as Level 2 versus Placebo.
- AEs will be arranged sorted in descending point estimate of the risk measure.

Tier 3: Standard safety output (no new outputs-see above).

It should be recognized that most studies are not designed to reliably demonstrate a causal relationship between the use of a pharmaceutical product and an adverse event or a group of adverse events. Except for select events in unique situations, studies do not employ formal adjudication procedures for the purpose of event classification. As such, safety analysis is generally considered as an exploratory analysis and its purpose is to generate hypotheses for further investigation. The 3-tier approach facilitates this exploratory analysis.

8.2.3.2. Laboratory Data (Hy's Law)

A listing of subjects who meet the criteria for Hy's law will be presented.

Abnormal values in aspartate transaminase (AST) and/or alanine transaminase (ALT) concurrent with abnormal elevations in total bilirubin that meet the criteria outlined below in the absence of other causes of liver injury are considered potential cases of drug-induced liver injury (potential Hy's Law cases) and should always be considered important medical events.

- Subjects with AST or ALT and total bilirubin baseline values within the normal range *who subsequently present with AST or ALT ≥ 3 times the upper limit of normal (X ULN) concurrent with a total bilirubin ≥ 2 X ULN with no evidence of hemolysis and an alkaline phosphatase ≤ 2 X ULN or not available.*
- *For subjects with preexisting ALT OR AST OR total bilirubin values above the upper limit of normal, the following threshold values should be used in the definition mentioned above:*
 - *For subjects with pre-existing AST or ALT baseline values above the normal range: AST or ALT ≥ 2 times the baseline values and ≥ 3 X ULN, or ≥ 8 X ULN (whichever is smaller).*

- ***Concurrent with***
 - *For subjects with pre-existing values of total bilirubin above the normal range: Total bilirubin increased by one time the upper limit of normal or ≥ 3 times the upper limit of normal (whichever is smaller).*

8.2.4. Summary of Efficacy Analyses

Endpoint	Analysis Set	Statistical Method	Model/ Covariates/ Strata	Output	Missing Data	Interpretation
Log _e (24-hour seizure rate +1) (DB Phase)	mITT	ANCOVA	Treatment, age strata, region and log-BL log-BL = Log _e (24-hour seizure rate +1) at baseline	Log-Scale - LS mean and 95% CI by treatment group, - LS mean difference from placebo, SE, 95% CI and p-value Original (Back Transformed) - LS Mean and 95% CI by treatment group - “Percent Change in Seizures” Relative to Placebo	OC	Primary Analysis
Log _e (24-hour seizure rate +1) (DB Phase)	ITT	ANCOVA	Treatment, age strata, region and log-BL	Log-Scale - LS mean and 95% CI by treatment group, - LS mean difference from placebo, SE, 95% CI and p-value Original (Back Transformed) - LS Mean and 95% CI by treatment group - “Percent Change in Seizures” Relative to Placebo	MI	Sensitivity Analysis
Log _e (24-hour seizure rate +1) (DB Phase)	mITT	Rank ANCOVA	Treatment, age strata, region and ranked log-BL	Log-Scale - Median by treatment group - LS mean difference from placebo, SE, 95% CI and p-value	OC	Sensitivity Analysis
Log _e (24-hour seizure rate +1) (DB Phase)	mITT	Wilcoxon-Mann Whitney Test		Log-Scale N, Mean, SD, Median, Min, Max, 25%, 75%, Test Statistics and p-value	OC	Sensitivity Analysis
Log _e (24-hour seizure rate +1)	mITT	Descriptive		N, Mean, SD, Median, Min,	OC	Evaluation for

Endpoint	Analysis Set	Statistical Method	Model/ Covariates/ Strata	Output	Missing Data	Interpretation
(BL, DB and Chg. from BL)		Statistics		Max, 25%, 75%, Skewness and Kurtosis		violations to model assumption
Log _e (24-hour seizure rate +1) (BL, DB and Chg. from BL)	mITT	Plot		Box Plot and Histogram of endpoint by Treatment Group	OC	Evaluation for violations to model assumption
Log _e (24-hour seizure rate +1) (DB Phase)	mITT	ANCOVA (Plot)	Treatment, age strata, region and log-BL	Residual Plot of Primary Analysis	OC	Evaluation for violations to model assumption
Responder Rate	mITT	Logistic Regression	Treatment, age strata, and region	Odds Ratio, 95% CI and p-value	OC	Secondary Endpoint
Responder Rate	mITT	Descriptive Statistics		N ¹ , n ² and %	OC	Secondary Endpoint
Raw Seizure Count	mITT	GLM	Assumption of a Poisson distribution and canonical log link function	Goodness of Fit, maximum likelihood estimates, least squares means, and p-values	OC	Supplemental Analysis

BL: Baseline, DB: Double Blind, OC: Observed Case, MI: Multiple Imputation, GLM: Generalized Linear Model

1: N is number of mITT subjects.

2: n is number of responder subjects.

